## **PROTOCOL:**

### **Study Purpose**

This project will evaluate a reward-based recovery management mobile app (PROCure Recovery), which seeks to address two ubiquitous problems facing Office-Based Opioid Treatment (OBOT)/Opioid Treatment Programs (OTP): (1) poor medication adherence/treatment retention, and (2) lack of standardized and valid outcomes monitoring systems to inform care.

Given the chronic, relapsing course of opioid use disorder (OUD), effective treatment requires long-term management. Treatment with buprenorphine is a viable option, associated with a variety of positive outcomes, including most notably, reductions in overdose mortality [3-12, 36]. Poor medication adherence is associated with program attrition, which in turn is linked to several negative outcomes [7, 12, 17-19]. Another widespread problem in OBOT/OTP settings is the relative absence of standardized and objective instruments. Although monitoring of treatment response is standard practice for many chronic medical conditions, addictions treatment providers have been slow to adopt these practices. Outcomes data collected from a standardized, valid, and reliable remote patient monitoring system holds great potential to drive clinical decision-making, and ultimately help payers, patients, and families identify programs from which patients have been empirically found to achieve remission. Despite the tremendous value in tracking patients post-detoxification and documenting outcomes, monitoring efforts are often hindered by relying on traditional methods and using existing staff to collect outcomes.

The proposed PROCure Recovery patient-facing mobile app will leverage the power of two established evidence-based approaches (i.e., contingency management and self-monitoring) to incentivize recovery and increase adherence to buprenorphine, engagement in care plans, as well as participation in routine outcomes monitoring. The PROCure Recovery mobile app offers providers real-time, clinically meaningful patient-reported outcomes data in accordance with best practices (measurement-based care) and national standards. Patients can earn both non-monetary and monetary-rewards (via funds deposited to a smart debit card blocking cash withdrawals and purchases at certain vendors) for medication adherence, engagement in care, and completing outcomes monitoring surveys. Remote adherence tracking and electronic outcomes monitoring extends care management and coordination outside the treatment facility or provider's office and into the patient's home. Based on trends in patient-reported outcomes collected remotely, providers can modify the care plan accordingly in real-time.

### **Study Aim**

Specific Aim: *Study preliminary effectiveness of PROCure Recovery on medication adherence, engagement in care, participation in remote patient monitoring, and clinical health outcomes.* A 4-week, randomized proof-of-concept pilot study will be conducted. Primary outcomes (and endpoints) include rates of: buprenorphine adherence (>90% daily doses; [14]), care plan adherence (>50% of weekly care plan activities; [53]), and participation in daily outcomes monitoring surveys (>90%; [44]) using a combination of patient/provider self-report and verification via app/dashboard, GPS location tracking data (to confirm attendance at outpatient appointments), and clinic urinalysis drug screen (UDS) results.

## Study Procedures & Statistical Analysis Plan

Recruitment: Patients will be recruited for the 4-week proof-of-concept trial from the South Florida Behavioral Health Network in Miami, FL. A targeted educational and recruitment in-service meeting will be conducted with the participating South Florida Behavioral Health Network opioid treatment program site, as facilitated by the President/CEO. The goal of the in-service meeting will be to make providers and clinical administrators aware of this project, and to assist in identifying eligible participants. Providers and administrators at the site will be informed about the purpose, procedures, risks, and benefits of the protocol, as well as the inclusion and exclusion criteria, so that they can best discuss the research project with individual staff and patients that might be eligible and interested, and make appropriate referrals to the research team for study inclusion.

Participants will be recruited by designated site staff under the direction of the PI. Treatment center intake staff will identify potential participants based on study inclusion/exclusion criteria and refer to research staff to confirm eligibility and enroll in the trial. Treatment staff will be made aware that participants must be  $>18$  years of age, own a smartphone, have a primary DSM-5 opioid use disorder diagnosis, be receiving buprenorphine, and cannot have any severe mental illness (e.g., schizophrenia) or other condition that would preclude them from participating. Research staff will conduct a second layer of verification (following referral from treatment staff) to ensure all participants are eligible and able to fully participate. To aid in recruitment and retention, all participants will be compensated for their time (see *Procedures* sections below for more information regarding compensation amount). Once participants are actively enrolled in the 4-week pilot study, research staff will maintain at least weekly personal contact with participants. The research team has relevant experience working with addictions treatment populations, and efficiently performing recruitment, screening, and follow-up to maintain participant flow and high follow-up rates. Recruitment and retention tracking will be reviewed on weekly study team conference calls so that potential recruitment shortfalls can be identified proactively and recruitment efforts broadened.

Procedures: A 4-week, randomized proof-of-concept pilot study will assess the feasibility, acceptability, and effectiveness of the PROCare Recovery app. Participating providers will be trained on the PROCare app prior to enrolling patients. Eligible patients will complete an electronic informed consent form prior to enrollment in the trial. Participants will complete baseline measures of study outcomes. Patients will be oriented to the app at the outset of treatment during the induction phase and continued throughout the 4-week trial. Remote patient outcomes data will be collected during treatment and at the end of the study via the PROCare app, which will include the same measures completed at baseline. Following 4-week participation, patients will be contacted to provide qualitative/quantitative feedback on PROCare usability.

Primary outcomes (and established endpoints) include rates of: buprenorphine adherence ( $>90\%$  daily doses [14]), care plan adherence ( $>50\%$  of weekly care plan activities [54]), and participation in daily outcomes monitoring surveys ( $>90\%$  [45]) using a combination of patient/provider self-report and verification via app/dashboard, clinic UDS results, and GPS location tracking data (to confirm attendance at outpatient appointments). Pre/post change in the secondary outcomes will be assessed using validated measures: opioid/other substance use (days of use), craving (Opioid Craving Scale [63]), motivation (Readiness Ruler [64, 65]), self-efficacy (Brief Situational Confidence Questionnaire [70]), quality of life (WHO EUROHIS Quality of Life Scale [66]), DSM-5 OUD diagnostic criteria [71], depression (Patient Health Questionnaire-9 [PHQ-9])/anxiety (General Anxiety Disorder-7 [GAD-7]). The System Usability

Scale [72] will be used to objectively quantify the usability of the PROCare prototype using a naive sample (Aim 2 sample is distinct from Aim 1 sample). Participants assigned to the PROCare group will also be asked to complete ultra-brief daily check-in measures. Additional information collected from PROCare participants will include activity data within the app (e.g., clicks, timing). Pre/Post data will be entered into a web form on tablet, laptop, or mobile device, and immediately sent (and stored), item-by-item, to the cloud platform that is hosted in a HIPAA secure physical and software environment. The entered data is visible to the participant in the screen of the device at that time, but is not stored locally.

Participants in both conditions (PROCare and treatment as usual/control) will receive \$50 for their study participation. As stated in the consent form, participants will only receive the \$50 gift card after they complete the 4-week follow-up. In order to receive the \$50, the participant must complete both the baseline and follow-up measures. Patients allocated to the PROCare group will have the opportunity to earn an additional \$150 in monetary incentives over the course of the 4-week trial based on their level of participation in various activities using the app (competing brief daily check-in surveys, reading psychoeducational materials in the content library, answering questions about adherence to their buprenorphine medication, attending treatment appointments, etc.). Participants in the PROCare group will receive monetary incentives using a smart debit card (*True Link*), which has a feature that can block purchases from certain vendors (liquor stores, etc.) and also block cash withdrawals. True Link smart debit cards have been used to good effect in numerous addiction treatment settings and similar reward-based research studies, and represent the most feasible option relative to cash payments. Due to randomization, participants will have an equal chance of being allocated to the PROCare group and having the opportunity to earn additional incentives. The amount of additional incentives for completing various activities within the app (\$150) is consistent with other similar reward-based substance use disorder apps.

**Statistical Analysis Plan:** Consistent with best practice guidelines for pilot trial sample size calculations with a medium effect size [73, 74] the proposed pilot study will attempt to include a minimum of 15 participants per arm. Accounting for an expected 30% attrition rate, we will attempt to recruit 40 patients. Independent samples t-tests and Pearson's chi-squared tests will determine mean differences on continuous and dichotomous variables, respectively.

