### **Specify study eligibility criteria.**

Patients/providers for pilot testing will be recruited through the South Florida Behavioral Health Network, Inc. in Miami, FL. Patients must be  $\geq$  18 years of age, own a smartphone, have a primary DSM-5 (APA, 2013) opioid use disorder (OUD) diagnosis, be receiving buprenorphine as part of their treatment, and no current suicidal ideation or severe mental illness (e.g., schizophrenia).

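### The app is said to start at buprenorphine induction, but eligibility admits any patient receiving buprenorphine, and neither the randomisation nor the analysis accounts for time on treatment

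*Combined protocol and SAP*

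**What the plan says.** In the combined protocol and SAP, under Study Procedures & Statistical Analysis Plan, the Procedures paragraph fixes when the app starts: "Patients will be oriented to the app at the outset of treatment during the induction phase and continued throughout the 4-week trial".

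The section Specify study eligibility criteria requires only that the patient "be receiving buprenorphine as part of their treatment". The Recruitment paragraph gives treatment staff the same open condition: patients must "have a primary DSM-5 opioid use disorder diagnosis, be receiving buprenorphine, and cannot have any severe mental illness". Neither place sets a maximum time on buprenorphine, a new-start requirement or a low-adherence requirement.

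On who finds patients, the Recruitment paragraph says "Treatment center intake staff will identify potential participants based on study inclusion/exclusion criteria". It also asks providers and administrators to refer patients, and allows recruitment to be widened if numbers fall short.

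On size, "the proposed pilot study will attempt to include a minimum of 15 participants per arm", and "Accounting for an expected 30% attrition rate, we will attempt to recruit 40 patients". Allocation is described only as giving an equal chance of either arm. The Statistical Analysis Plan paragraph names independent-samples t-tests and Pearson chi-squared tests, with no stratification factor and no covariate.

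**The concern.** A patient well into buprenorphine treatment meets the written criteria but cannot be oriented to the app during induction. The criteria and the procedures therefore describe populations of different breadth, and a reader cannot tell which one the pilot estimate is for.

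Time on treatment plausibly matters for the outcome. One primary endpoint is taking more than 90% of daily doses over 4 weeks. Patients who have stayed in treatment may already meet it more often and so have less room to gain. With about 40 patients, allocation that ignores this factor can leave the arms visibly different on it, and an unadjusted test cannot correct for that.

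**Working it through.** **Inputs from the documents.** Minimum 15 per arm, 30% attrition, 40 recruited, 1:1 allocation, unadjusted tests.

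**Inputs assumed.** The documents give neither the share of new starters nor any adherence rate by time on treatment. I assume exact 20:20 allocation, half the patients new, and control-arm rates of meeting the dose endpoint of 50% in new starters and 70% to 90% in established patients.

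**Step 1: the plan's own figure.** 15 × 1.3 = 19.5, rounded up to 20 per arm, gives the stated 40. Dividing by the retained fraction instead gives 15/0.7 = 21.4, so 22 per arm or 44 in all. That is a separate matter; here I take 20 per arm as planned.

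**Step 2: chance imbalance.** Let X be the number of new starters among the 20 app patients, when 20 of 40 are new. X is hypergeometric (40, 20, 20). The gap in share between arms is (2X − 20)/20, so a gap of at least 20 points means |X − 10| ≥ 2.
- P(X = 10) = C(20,10)²/C(40,20) = 0.248
- P(X = 9) = P(X = 11) = C(20,9)·C(20,11)/C(40,20) = 0.205
- P(gap ≥ 20 points) = 1 − 0.248 − 2 × 0.205 ≈ 0.34 (0.343 unrounded)

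If a quarter are established instead of half, the figure is 27%. This step needs the mix but no adherence rate.

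**Step 3: what a 20-point gap does.** Shift in the adherence difference = gap × (established rate − new-starter rate).
- Established 90%: 0.20 × (0.90 − 0.50) = 8 points
- Established 70%: 0.20 × (0.70 − 0.50) = 4 points

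**Step 4: precision gained by stratifying** (20 per arm, half new, control rates used in both arms).

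| Established rate | Pooled rate | Total variance | Within-stratum variance | SE unstratified | SE stratified | Reduction |
|---|---|---|---|---|---|---|
| 90% | 70% | 0.7 × 0.3 = 0.21 | 0.5 × 0.25 + 0.5 × 0.09 = 0.17 | √(2 × 0.21/20) = 14.5 points | √(2 × 0.17/20) = 13.0 points | about 10% |
| 70% | 60% | 0.6 × 0.4 = 0.24 | 0.5 × 0.25 + 0.5 × 0.21 = 0.23 | √(2 × 0.24/20) = 15.5 points | √(2 × 0.23/20) = 15.2 points | about 2% |

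The 8-point shift is 8/14.5, or about half a standard error.

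**Step 5: dilution, illustration only.** With half of each type, the pooled effect is the average of the two effects. If the app gains 25 points in new starters (50% to 75%) and 5 in established patients (90% to 95%), the pooled gain is 0.5 × 25 + 0.5 × 5 = 15 points. If both groups gain equally, there is no dilution. The documents cannot tell these cases apart.

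**The case against.** The strongest reply is that the passages can be read together. A patient in induction is receiving buprenorphine, so the Procedures sentence may simply narrow when the app starts. Intake staff normally meet new admissions, and nothing says that long-stable patients are expected. This stands in part: most enrolees may well be new. It does not close the gap, because intake staff and the research team's second check both apply criteria with no time limit, and providers may also refer. If the outset of treatment means the start of the study, then the induction phase is left undefined.

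Four stronger readings are tempting, and the documents do not support them:
- **That imbalance would bias the trial.** Under 1:1 randomisation it is sampling variation in either direction, already reflected in the standard error of the unadjusted comparison.
- **That established patients are known to be near the ceiling.** The Background section reports how long patients remain adherent (fewer than half for at least 90 days, 31% beyond a year). It gives no share of daily doses taken by those who stay.
- **That the early fall in use and craving among new starters would be credited to the app.** The control arm has the same expected course, and the plan compares arms.
- **That different sites would apply different rules.** The Recruitment paragraph describes one participating site and one research team.

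Two further points stand. The ceiling argument touches one of three primary outcomes; nothing suggests it applies to care-plan adherence or survey participation. And dilution is a loss only if new starters are the target. Broad eligibility is a legitimate choice for a proof-of-concept pilot, and the pooled effect would then be the right quantity.

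**Conclusion.** The point holds as a modest, inexpensive improvement. The criteria permit a mix of new and established patients that the induction sentence does not foresee, and neither allocation nor analysis takes it into account. The validity of the randomised comparison is not threatened.

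The one figure that does not depend on adherence rates is the 34% chance of a gap of at least 20 points, which rests on half of 40 patients being new and 20:20 allocation. The 4- to 8-point shift and the 2% to 10% reduction in standard error rest on assumed control rates and shrink as the two groups become more alike. If nearly all enrolees prove to be new, the practical effect is small and what remains is the unclear population. The size of any dilution is unknown.

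**What to change.** Reconcile the Recruitment paragraph, the Procedures paragraph and the eligibility section on whether enrolment is limited to patients in induction. That choice belongs to the sponsor. Restricting entry may slow recruitment; leaving it open broadens the population that the estimate describes.

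If entry stays open:
1. Record the buprenorphine start date with the pre-study log of current medications, which the section on monitoring progress and reporting adverse events already plans. That section does not mention a start date.
2. Stratify the 1:1 randomisation by new start versus established, using a cut-off set in advance, with blocks within each stratum. Simple randomisation within strata would not balance them.
3. Include the stratum in the between-arm comparison, for example Cochran-Mantel-Haenszel for the dichotomous outcomes and a linear model with arm and stratum for the continuous ones.
4. Show results by stratum descriptively, without subgroup testing.

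The cost is one extra baseline date and slightly more complex allocation and analysis. This option needs no extra patients.

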OBOT/OTP settings often fail to use standardized/objective instruments. Without formal, psychometrically sound measures, providers are unable to document outcomes and quantitatively demonstrate any kind of meaningful impact. The adoption of a measurement-based care system is required for all treatment providers, irrespective of level of care. The top two national accrediting bodies, *The Joint Commission* [46] and *CARF International*, now seek evidence of compliance to this outcome measures standard and describe requirements for a reliable performance measurement system. All of the items included in the PROCare app are valid and backed by empirical research, thereby ensuring providers are in compliance with national standards. With PROCare, many tasks of measurement-based care are automated, and patients are incentivized to provide clinically-meaningful outcomes data using the app, which can be reviewed by the provider in real-time using the clinical dashboard to inform care.

**Preliminary Studies:** [name] (PI) has been involved in relevant addictions outcomes work through his role as an expert advisor and researcher to several agencies ranging from individual OTPs to national health care organizations. [name] has led a number of studies focused on solutions to increase adherence to care plans and their impact on outcomes [54-56], and has published numerous articles involving opioid medication treatment populations [15, 57-60]. He frequently consults with treatment agencies (buprenorphine clinics) on measurement-based care and improving their systems through recovery monitoring. Preliminary results from [name] research show that protracted care plan management—delivered via telephone—is associated with high rates of abstinence, adherence, and quality of life up to 1 year after treatment [56]. These favorable but preliminary indications of the effectiveness of telephone-based care management require replication in a well-powered study. Investigation of alternative, more acceptable digital health solutions (mobile app) is warranted; the proposed project will fill these gaps.

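### The protocol gives two unreconciled routes for the week-4 measures, the PROCare app and a web form, and does not require one mode for both arms

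*Combined protocol and SAP*

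**What the plan says.** All of the collection rules are in the Procedures paragraphs of Study Procedures & Statistical Analysis Plan.

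- **App route.** "Remote patient outcomes data will be collected during treatment and at the end of the study via the PROCare app". No arm is named. On content, the same sentence describes these data as something "which will include the same measures completed at baseline".
- **Web-form route.** "Pre/Post data will be entered into a web form on tablet, laptop, or mobile device", with the entries sent to a secure cloud platform. Again no arm is named.
- **What the measures are for.** "Pre/post change in the secondary outcomes will be assessed using validated measures". Eight domains are listed: days of opioid or other substance use, craving, motivation, self-efficacy, quality of life, DSM-5 opioid use disorder criteria, depression and anxiety.
- **Who is followed up.** "Participants in both conditions (PROCare and treatment as usual/control) will receive" $50, and to be paid, "the participant must complete both the baseline and follow-up measures".
- **What is limited to one arm.** "Participants assigned to the PROCare group will also be asked to complete ultra-brief daily check-in measures". In-app activity data are limited to that group in the same way.

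The background section describes the data that patients enter in the app as information "which can be reviewed by the provider in real-time using the clinical dashboard to inform care".

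**The concern.** A randomised comparison of self-reports is safe only if both arms are asked in the same way. Here one sentence puts the week-4 measures in the app, which is the intervention itself, and another puts them in a form that needs no app. The protocol never says which arm uses which, or whether the two are the same instrument.

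The app is not described as a neutral questionnaire. Study Purpose says patients can earn rewards for completing monitoring surveys and that providers can adjust care plans in response to the data. The background section says providers see the entries as they arrive. Days of use, craving, disorder criteria, depression and anxiety are sensitive answers, and a patient may give them differently to a treating provider than to a research team.

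If mode differs by arm, all eight secondary domains are exposed at once, and the problem cannot be repaired after data collection.

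**Working it through.** The plan states no figure on this point, so there is none to reproduce. The check sets the sentences side by side and follows each reading that the text permits.

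**Step 1: do the two sentences cover the same data?** The app sentence covers the end-of-study measures, with the same content as baseline. The web-form sentence covers pre/post data. The secondary outcomes are defined as pre/post change. Both sentences therefore claim the week-4 secondary measures.

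**Step 2: does any other text decide between them?** The payment rule shows that both arms are to be followed up, but not by what route. The explicit limits to the PROCare group concern daily check-ins and app activity, not the week-4 measures. App orientation is described for patients generally, with no arm named. Nothing settles the mode.

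**Step 3: what does each workable reading imply?**

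| Week 4, PROCare arm | Week 4, control arm | Consequence |
|---|---|---|
| Web form | Web form | Same mode; clean comparison. Permitted, but it requires setting the app sentence aside. |
| App | Web form | Mode coincides with arm. |
| App | App, supplied for assessment | Same mode, but controls receive part of the intervention. The background section treats self-monitoring as effective in its own right. |
| One instrument reached through either | The same instrument | Possibly the same mode; whether reward and dashboard functions apply is unstated. |

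**Step 4: what would the second row do to the estimate?** Let a be the average reporting shift in the app and w the shift in the web form. Let P and C be the true mean changes in the PROCare and control arms. Take baseline as web form in both arms.

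- Observed mean change, PROCare: (P + a) − w if measured from a true baseline of zero, that is P + (a − w).
- Observed mean change, control: C + (w − w) = C.
- Observed difference: (P − C) + (a − w).

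Subtracting baseline does not remove a − w, because only one arm changes mode. Within each arm the week-4 mode does not vary, so a mode covariate would be identical to the arm indicator and no adjustment could estimate it. The analysis plan offers only independent-samples t-tests and Pearson chi-squared tests, which return the sum.

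**Step 5: how large is a − w?** The documents give no value, range or direction for it.

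**The case against.** The strongest reply is that the text already supports a common web form. The secondary outcomes are pre/post measures, the web-form sentence names pre/post data without restricting the arm, and where this paragraph means one arm it says so. The form and the app may also belong to one system. The background section says the BH-Works cloud platform and web tools underlie PROCare, and Privacy & Confidentiality says all clinical data are stored in the BH-Works cloud.

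This stands as far as it goes: a common mode is permitted, and may be what was meant. It is not required, because the app sentence is equally unrestricted and is a positive statement about the end of the study.

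A second reply concerns what is special about the app, and it also stands in part. Risks & Benefits limits access to study data to the research team, which sits uneasily with provider review. The listed ways of earning the extra $150 do not name the week-4 measures, although the list is open-ended. The payment expressly tied to follow-up is the $50 common to both arms. A reader might infer that PROCare patients would answer week 4 for a reward and in view of their provider; the documents do not establish either.

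**Conclusion.** The point holds as an unreconciled instruction that leaves room for a bias between arms. It does not show that a biased procedure is planned. Its reach is every self-reported secondary outcome, and its size cannot be derived from the documents. It rests on one inference: that a treatment-as-usual arm does not have the app. If controls are given the app for assessment, the difficulty becomes exposure of controls to part of the intervention.

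Three stronger readings are tempting and should not be drawn:

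- **Controls have no week-4 data.** The app sentence alone might suggest this for the roughly 20 controls (40 recruits, equal allocation: 40 / 2 = 20). The payment rule contradicts it, since follow-up is required in both conditions, and the web form gives controls a route.
- **PROCare patients certainly switch from web form to app.** The web-form sentence covers the post data as well as the pre data, so a switch is only one possible reading.
- **The bias is a given fraction of a medium effect.** No section supports a figure for the reporting shift, so any such fraction would be an assumption divided by another.

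This is a pilot and the primary outcomes are not at issue here, which limits the weight. The change is still worth making before data collection.

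**What to change.** Replace the app sentence in the Procedures paragraph with:

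> *In both arms, the baseline and week-4 batteries are completed in the same research web form, outside the app's reward and provider-dashboard functions. For the secondary outcomes, data collected in the app during treatment are engagement and process data for the PROCare arm only.*

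The second sentence is confined to the secondary outcomes because the primary outcomes draw on app and dashboard verification, which this change is not meant to alter.

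The cost is small. The protocol already describes the web form, so the change is mainly one of wording. If the form turns out to be delivered inside the app's own system, reward and dashboard display would have to be switched off for these two assessments. PROCare patients would open a separate form at week 4.

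### Three unranked primary outcomes and no rule for which one supports preliminary effectiveness; one of them, survey participation, has no evident control-arm value

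*Combined protocol and SAP*

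**What the plan says.** The Study Aim section sets the purpose: "Study preliminary effectiveness of PROCure Recovery on medication adherence, engagement in care, participation in remote patient monitoring, and clinical health outcomes". It then lists the endpoints: "Primary outcomes (and endpoints) include rates of: buprenorphine adherence (>90% daily doses; [14]), care plan adherence", followed by survey participation. The Procedures paragraph of Study Procedures & Statistical Analysis Plan repeats the same three, beginning "Primary outcomes (and established endpoints) include rates of: buprenorphine adherence" and ending "and participation in daily outcomes monitoring surveys". The thresholds are above 90% of doses, above 50% of weekly care plan activities and above 90% of surveys. The secondary outcomes are listed separately, but nothing orders the three primaries.

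The Statistical Analysis Plan paragraph consists of a sample size statement and one sentence on tests: "Independent samples t-tests and Pearson's chi-squared tests will determine mean differences on continuous and dichotomous variables, respectively". It gives no significance level, sidedness, testing order, multiplicity adjustment, rule on whether one or all primaries must favour the app, or criterion for success.

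On data collection, the Procedures paragraph says: "Participants assigned to the PROCare group will also be asked to complete ultra-brief daily check-in measures". The payment text that follows lets only the app group earn a further $150, and completing the daily check-ins is one of the activities that earns it.

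**The concern.** Once hypothesis tests are used to support a statement about effectiveness, the plan has to say which result carries it. Here the choice stays open until the data are in: one primary outcome, a majority, or all three could be taken as the standard.

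The choice matters because the outcomes mean different things. Doses taken is close to the clinical purpose. Attendance at care plan activities is a step away from it. Completing surveys that the app prompts and pays for is a measure of engagement with the intervention itself. A pilot could be reported as positive on the last of these while buprenorphine adherence showed nothing. That would mislead whoever decides whether to go on to a larger trial.

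**Working it through.** **Inputs from the documents.** Three primary outcomes (Study Aim; Procedures). Separate t-tests or chi-squared tests (Statistical Analysis Plan). Equal chance of allocation, and a minimum of 15 per arm (Study Procedures & Statistical Analysis Plan). The plan states no error rate, so there is no figure of its own to reproduce.

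**Assumptions.** Each test is two-sided at 5%, so 2.5% lies in the app's favour. The app has no effect on the outcomes tested.

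**Step 1: which outcomes can be compared between arms.** Buprenorphine adherence and care plan adherence can in principle be measured in both arms. Daily check-ins are described for the app group only, and no control-arm counterpart is described. If survey participation is not compared, two tests remain. If controls are counted as non-participants, the difference is built in and a calculation under no effect does not apply. The three-test figures below hold only if some comparable control measure exists.

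**Step 2: at least one false significant result, independent tests.**

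| Tests | In the app's favour | Either direction |
|---|---|---|
| 1 | 2.5% | 5% |
| 2 | 1 − 0.975² = 4.9% | 1 − 0.95² = 9.75% |
| 3 | 1 − 0.975³ = 7.3% | 1 − 0.95³ = 14.3% |

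**Step 3: correlated outcomes.** Patients who take their doses probably also attend more, so positive correlation is likely. Simulation of equally correlated normal test statistics (2,000,000 draws) gives:

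| Correlation | 2 tests, app's favour | 3 tests, app's favour | 3 tests, either direction |
|---|---|---|---|
| 0.3 | 4.8% | 6.8% | 13.6% |
| 0.5 | 4.6% | 6.3% | 12.6% |
| 0.7 | 4.2% | 5.5% | 10.9% |
| 0.9 | 3.5% | 4.2% | 8.4% |

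**Step 4: sensitivity.** With three independent tests at an assumed level of 1% or 10%, the either-direction figure is 3.0% or 27.1%. The Pearson chi-squared test is not exactly 5% in small samples. At 15 per arm its exact size over the true rates checked (10% to 90%) runs from 2.5% to 5.5%, which gives 7.2% to 15.6% over three independent tests.

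**Step 5: effect of the fix.** One designated primary outcome restores 2.5% in the app's favour (5% in either direction). Holm across two between-arm primaries keeps the either-direction rate at or below 5%. Taking the plan's medium effect as a standardised difference of 0.5 (an assumption; the plan gives no number), a t-test with 15 per arm has about 26% power at 5% and about 18% at Holm's first step of 2.5%.

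**The case against.** The strongest defence is that this is a four-week proof-of-concept pilot, sized by pilot guidelines ("Consistent with best practice guidelines for pilot trial sample size calculations with a medium effect size"), which claims only preliminary effectiveness. Pilots that report feasibility and estimates often go without multiplicity control, and reporting all three estimates with confidence intervals and no success claim would be reasonable. This lowers the urgency. It does not remove the point, because the stated aim is effectiveness and the only analysis named is significance testing.

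The preference for buprenorphine adherence can also be questioned. The Study Purpose section names two problems, and survey participation addresses the second. Being listed first is not a declared priority. That is fair: the sponsor may choose otherwise, provided the choice is made before data are seen and the outcome can be compared between arms.

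Two stronger readings are tempting and are not supported:

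- A reader might infer a 14% chance of a false success. That figure needs three independent two-sided 5% tests, which the plan never states. It also counts differences favouring control, and it treats survey participation as an outcome to which no effect could apply.
- A reader might count about nine secondary outcomes, add the three primaries and reach 46% (1 − 0.95¹²). The count depends on how the paired items in the list are split. The Procedures paragraph describes the secondaries as pre/post change, so a between-arm test of each is inferred. Independence among craving, mood, quality of life and substance use is also implausible.

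**Conclusion.** The concern holds in a limited form. The plan has three unranked primary outcomes, an effectiveness aim and no decision rule; that gap does not depend on any percentage. The numerical cost is moderate. For the two outcomes comparable between arms, the false-positive chance in the app's favour roughly doubles, from 2.5% to 4.9%. If three could be tested it would be about 6% to 7% for correlations up to 0.5, and lower with stronger correlation. All of this assumes two-sided 5% tests.

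Survey participation is better seen as a comparability fault than as a multiplicity one. No error-rate adjustment would make an app-only, paid activity into evidence against control. The pilot is not invalidated, but its effectiveness statement would be hard to interpret as the plan stands, and the repair is cheap.

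**What to change.** 1. In Study Aim and in Procedures, name one between-arm primary outcome before any data are seen. Buprenorphine adherence is the natural candidate: it is listed first in both places and matches the first problem in Study Purpose.
2. Make care plan adherence secondary.
3. Report survey participation descriptively in the app arm as an engagement measure, not as evidence of effectiveness.
4. In the Statistical Analysis Plan paragraph, state the significance level and sidedness. Say that the preliminary effectiveness statement rests on the primary outcome, with all other outcomes given as supportive estimates with confidence intervals.
5. If two between-arm primaries are kept, apply Holm across them.

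The cost is a few sentences, with no change to sample size, data collection or patient burden. The downside is that a good result on care plan adherence alone would no longer count as success. Holm, if used, would lower power that is already low (about 26% to about 18% at the first step, on the assumptions above).
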